5.1.3 Replacement of Subjects

Subjects who miss \geq 20% of the planned doses of ibrutinib or venetoclax for reasons other than toxicity (eg, non-compliance, withdrawal of consent, disease progression) during the TLS and DLT assessment period (venetoclax ramp-up during the Safety Run-in Period), or subjects who do not complete the TLS and DLT assessment period for any reason other than TLS or a DLT will be replaced.

Randomized subjects will not be replaced in the Randomization Phase.

5.1.4 Treatment-naive Open-label Arm

In the treatment-naive open-label arm, approximately 75 subjects will be enrolled and treated with ibrutinib 560 mg and venetoclax 400 mg. Among them, approximately 50 subjects ≥ 65 years and approximately 25 subjects with a TP53 mutation will be enrolled. Ibrutinib and venetoclax will be administered using the 5-week ramp-up schedule.

Subject eligibility will be determined up to 28 days prior to the first dose of study drug.

After written informed consent has been obtained and eligibility has been established, the study site will obtain the subject's identification number from the Interactive Response Technology (IRT) System.

Subjects in the protocol-defined increased-risk for tumor lysis syndrome (TLS) group will be hospitalized for a minimum of 24 hours (and up to 48 hours at the discretion of the investigator) at the start of the 20 mg and 50 mg ramp-up dose of venetoclax for monitoring and prophylaxis of TLS; subjects in the low-risk for TLS group may be hospitalized at the discretion of the investigator.

Subjects will be treated with ibrutinib and venetoclax for approximately 104 weeks (2 years), followed by ibrutinib monotherapy until PD, unacceptable toxicity or withdrawal of consent. Venetoclax will be discontinued after 104 weeks (2 years) of treatment, regardless of response assessment.

Subjects who discontinue study treatment for any reason will be followed for disease progression, subsequent anticancer therapy, and survival status until study closure.

5.2 Study Treatment

5.2.1 SRI and Randomized Phase

Ibrutinib

• Orally once daily ibrutinib 560 mg (4 x 140 mg capsules OR 1 x 560 mg tablet) continuously

Note: Dose modification of ibrutinib for AEs is specified in Section 5.3.1.4, Section 5.3.1.6, and Section 6.2.1.1.

Important: If using tablets, please ensure that patients do not take more than one 560 mg tablet per day.

Venetoclax

• Orally once daily venetoclax at a target dose of 400 mg (4 X 100 mg)

Note: Dose modification of venetoclax/placebo for AEs is specified in Section 5.3.2.5 and Section 6.2.1.2.

Placebo

• Oral once daily matching placebo for venetoclax at a target dose of 400 mg (4 X 100 mg)

Note: Dose modification of venetoclax/placebo for AEs is specified in Sections 5.3.2.5 and Section 6.2.1.2.

5.2.2 Treatment-naive Open-label Cohort

Ibrutinib

• Orally once daily ibrutinib 560 mg (4 x 140 mg capsules OR 1 x 560 mg tablet) continuously

Note: Dose modification of ibrutinib for AEs is specified in Section 5.3.1.4, Section 5.3.1.6, and Section 6.2.1.1.

Important: If using tablets, please ensure that patients do not take more than one 560 mg tablet per day.

Venetoclax

• Orally once daily venetoclax at a target dose of 400 mg (4 X 100 mg) dosed concurrently with ibrutinib

Note: Dose modification of venetoclax/placebo for AEs is specified in Section 5.3.2.5 and Section 6.2.1.2.

5.3 Study Medication

5.3.1 Ibrutinib

5.3.1.1 Formulation/Packaging/Storage

Ibrutinib is provided either as hard gelatin capsules each containing 140 mg of ibrutinib, or as film coated tablets each containing 560 mg of ibrutinib. All formulation excipients are compendial and are commonly used in oral formulations. Refer to the ibrutinib IB for a list of excipients.

The ibrutinib capsules will be packaged in opaque high-density polyethylene plastic bottles with labels bearing the appropriate label text as required by governing regulatory agencies and child-resistant packaging. The ibrutinib tablets 560 mg will be packaged in blisters.

Refer to the Pharmacy Manual/site investigational product manual for additional guidance on dose modifications for subjects on ibrutinib tablets, study drug storage, preparation and handling.

Study drug labels will contain information to meet the applicable regulatory requirements.

5.3.1.2 Dose and Administration

Ibrutinib 560 mg (4 x 140 mg capsules or 1 x 560 mg tablet) is administered orally once daily. The ibrutinib capsules or tablet are/is to be taken with venetoclax/placebo tablets at approximately the same time each day with a meal and water. The capsules or tablet should be swallowed intact and subjects should not attempt to open capsules, break the tablet or dissolve

them in water. The use of strong CYP3A inhibitors/inducers, and grapefruit and Seville oranges should be avoided for the duration of the study (Appendix D).

If a dose is not taken at the scheduled time, it can be taken as soon as possible on the same day with a return to the normal schedule the following day. The subject should not take extra capsules to make up the missed dose.

For subjects starting with the concurrent administration of ibrutinib and venetoclax using the standard Ramp-up Schedule, ibrutinib will be delivered in the clinic on Days 1, 2 (all subjects) and 3 (hospitalized subjects) of Weeks 1 and 2; on Days 1 of the remaining weeks during the venetoclax Ramp-up Period (see Section 8.2); and on the PK sample collection day (see Section 7.1.4.1 and Section 7.1.4.2). Otherwise, ibrutinib dosing is typically done on an outpatient basis.

Ibrutinib will be dispensed to subjects at each dispensing visit. Study drug may not be shipped to the subject without approval from the Sponsor and may not be dispensed to anyone other than the subject. Unused ibrutinib dispensed during previous visits must be returned to the site and drug accountability records (Section 12.8) updated at each visit. Returned drug must not be redispensed to anyone and must not be destroyed without prior written approval of Clinical Monitor/CRA and /or the Sponsor. Study drugs can only be destroyed after full accountability and reconciliation by the Clinical Monitor/CRA unless required by local institutional policy.

5.3.1.3 Overdose

There is no specific experience in the management of ibrutinib overdose in patients. No MTD was reached in the Phase 1 study in which subjects received up to 12.5 mg/kg/day (1400 mg/day). Healthy subjects were exposed up to a single dose of 1680 mg. One healthy subject experienced reversible Grade 4 hepatic enzyme increases (AST and ALT) after a dose of 1680 mg. Subjects who ingested more than the recommended dosage should be closely monitored and given appropriate supportive treatment.

Refer to Section 11.3 for further information regarding special reporting situations as a result of overdose.

5.3.1.4 Dose Modification for Adverse Reactions

Ibrutinib interruption and/or dose reduction may be required for toxicities related to ibrutinib. The dose of study drug must be modified according to the dose modification guidance in Table 1 and Table 2 if any of the following ibrutinib related toxicities occur:

- Grade 3 or greater neutropenia with infection or fever
- Grade 4 neutropenia (ANC $< 500/\mu$ L) for more than 7 days. See Section 6.1 for instructions regarding the use of growth factor support.

- Grade 3 thrombocytopenia (platelets $< 50,000/\mu L$) in the presence of Grade ≥ 2 bleeding
- Grade 4 thrombocytopenia (platelets < 25,000/μL)
- Grade 3 or greater non-hematological toxicity (Note: Table 2 recommendations for Grade 3 or greater cardiac failure and cardiac arrhythmias)
- Grade 2 cardiac failure (Table 2)
- Any other Grade 4 or unmanageable Grade 3 toxicity

If clinically indicated, the use of anticoagulants or antiplatelet agents may be considered for the thromboprophylaxis of atrial fibrillation (Section 6.2.4 and Section 1.2.4.6).

For other AEs including grade 2 AEs that are deemed per the investigator potentially manageable by dose reduction, these can be managed with a one dose level dose reduction.

In the event that the investigator feels deviation from the recommendations above is required, please consult the medical monitor to discuss for approval.

Dose changes must be recorded in the Dose Administration eCRF.

Table 1. Ibrutinib Dose Modifications

Hematologic AEs			
Occurrence	Action to be Taken		
First	Withhold ibrutinib until recovery to an ANC \geq 750/ μ L or platelets \geq 25,000/ μ L with no evidence of Grade \geq 2 bleeding; may restart at original dose level		
Subsequent	Withhold ibrutinib until recovery to an ANC $\geq 750/\mu L$ or platelets $> 25,000/\mu L$ with no evidence of Grade ≥ 2 bleeding; may restart at 1 dose level lower* (refer to Table 3)		
Other Hematologic and Non-Hematologic AEs (for Events not Specified in Table 2)			
Occurrence	Action to be Taken		
First	Withhold ibrutinib until recovery to Grade ≤ 1 or baseline; may restart at original dose level ^a		
Second	Withhold ibrutinib until recovery to Grade ≤ 1 or baseline; restart at 1 dose level lower* (3 capsules [ie 420 mg daily]) (refer to Table 3)		
Third	Withhold ibrutinib until recovery to Grade ≤ 1 or baseline; restart at 1 dose level lower (2 capsules [ie 280 mg daily]) (refer to Table 3)		
Fourth	Discontinue ibrutinib		

When resuming treatment, restart at the same or lower dose based on benefit-risk evaluation. If the toxicity reoccurs, reduce daily dose by 140 mg.

^{*} Dose reduction due to a TLS event or a DLT is not applicable for Safety Run-in subjects.

Note: Do not dose below 280 mg daily except in case of required concomitant administration of strong or moderate CYP3A inhibitors or moderate hepatic impairment; refer to Section 5.3.1.6 and Section 6.2.1.

Table 2. Ibrutinib Dose Modifications for Cardiac Failure or Cardiac Arrhythmias

Events	Occurrence	Action	
	First	Hold study drug until recovery to Grade ≤ 1 or baseline; restart at 1 dose level lower (3 capsules [ie, 420 mg daily])	
Grade 2 cardiac failure	Second	Hold study drug until recovery to Grade ≤ 1 or baseline; restart at 1 dose level lower (2 capsules [ie, 280 mg daily])	
	Third	Discontinue study drug	
Grade 3 cardiac	First	Hold study drug until recovery to Grade ≤ 1 or baseline; restart at 1 dose level lower (3 capsules [ie, 420 mg daily]) ^a	
arrhythmias	Second	Discontinue study drug	
Grade 3 or 4 cardiac failure			
Grade 4 cardiac	First	Discontinue study drug	

a Evaluate the benefit-risk before resuming treatment.

Table 3. Ibrutinib Dose Reduction Levels

Starting Dose Level	560 mg
Dose Reduction Level 1	420 mg
Dose Reduction Level 2	280 mg
Dose Reduction Level 3	140 mg
Dose Reduction Level 4	Discontinue

For required dose modification for hepatic impairment refer to Section 5.3.1.6 and for concomitant treatment with CYP3A inhibitors refer to Section 6.2.1.

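### For repeat hematologic AEs, Tables 1 and 3 together step ibrutinib from 280 mg to 140 mg, a dose the note under Table 1 bars, and no permitted step after recovery is stated at 280 mg

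*Protocol*

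**What the plan says.** Protocol 5.3.1.4 requires ibrutinib to be modified under Tables 1 and 2 when listed toxicities occur. The hematologic triggers are neutropenia of Grade 3 or more with infection or fever, Grade 4 neutropenia beyond 7 days, Grade 3 thrombocytopenia with bleeding of Grade 2 or more, and Grade 4 thrombocytopenia.

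- **Table 1, hematologic block.** There are two rows. After the first event the drug is withheld until recovery and may restart at the original level. After every later event it is withheld until recovery and "may restart at 1 dose level lower* (refer to Table 3". No row limits the number of reductions or ends in discontinuation.
- **Table 3.** The levels are 560, 420, 280 and 140 mg, then discontinue. The 140 mg level is "Dose Reduction Level 3"; discontinuation is "Dose Reduction Level 4".
- **Note under Table 1.** "Do not dose below 280 mg daily except in case of required concomitant administration of strong or moderate CYP3A inhibitors or moderate hepatic impairment".
- **Table 1, other-AE block.** The third event says "restart at 1 dose level lower (2 capsules [ie 280 mg daily]) (refer to Table 3"; the fourth event is discontinuation.
- **Table 2, Grade 2 cardiac failure.** The second event says "restart at 1 dose level lower (2 capsules [ie, 280 mg daily"; the third event is discontinuation.
- **Separate uses of 140 mg.** The sentence under Table 3 reads "For required dose modification for hepatic impairment refer to Section 5.3.1.6 and for concomitant treatment with CYP3A inhibitors refer to Section 6.2.1". Section 5.3.1.6 uses 140 mg for Child-Pugh class B arising on study, and 6.2.1.1 uses it with strong or moderate CYP3A inhibitors.
- **Subjects who start at 280 mg.** Section 5.3.1.6 sets this starting dose for chronic Child-Pugh class A impairment at enrollment.

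**The concern.** A site that follows the hematologic row into Table 3 arrives at a dose that the same section prohibits. A site that gives the note priority knows it must withhold, but has to work out for itself whether ibrutinib then stops or resumes at 280 mg.

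What is at stake is safe and uniform dosing after repeated neutropenia or thrombocytopenia. Cytopenias are a named ibrutinib risk (Protocol 1.2.4.4) and neutropenia is an important identified venetoclax risk (1.3.3.2), so the situation is foreseeable. One event could be recorded as a dose reduction at one site and a discontinuation at another. Both feed a listed safety endpoint (Protocol 10.2.3), and SAP Table 3 summarizes the two separately.

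**Working it through.** The plan states no figure to reproduce, so the check applies the rules to the dose levels.

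**Inputs.** Starting doses are 560 mg (5.3.1.2) or 280 mg for Child-Pugh class A (5.3.1.6). Table 3 levels are 140 mg apart. The floor is 280 mg (note under Table 1).

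**Assumption.** For a subject whose dose has already been lowered for another AE, the original dose level in the first hematologic row is taken as the dose held at that event.

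**Rule.** With S the dose held at the first hematologic event, the first event leaves S unchanged and each later one takes off 140 mg. The dose after event k is S − 140 × (k − 1). It first falls below 280 mg when k > 1 + (S − 280)/140:

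- S = 560: k > 1 + 280/140 = 3, so the 4th event.
- S = 420: k > 1 + 140/140 = 2, so the 3rd event.
- S = 280: k > 1 + 0/140 = 1, so the 2nd event.

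| Dose held at first hematologic event | Event 1 | Event 2 | Event 3 | Event 4 | Event 5 |
|---|---|---|---|---|---|
| 560 mg, no other reduction | 560 | 420 | 280 | **140, barred** | Discontinue |
| 420 mg, after one other-AE reduction | 420 | 280 | **140, barred** | Discontinue | – |
| 280 mg, Child-Pugh A start or two other-AE reductions | 280 | **140, barred** | Discontinue | – | – |

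140 mg is barred in each case unless the subject also has a required strong or moderate CYP3A inhibitor or moderate hepatic impairment. Child-Pugh class A is mild impairment, so it does not qualify.

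**Comparators.** The other-AE rows from 560 mg give 560, 420, 280, then discontinue at event 4. Grade 2 cardiac failure gives 420, 280, then discontinue at event 3. Neither goes below 280 mg.

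**Does another sentence settle it?** A footnote to Table 1 calls for a 140 mg cut if toxicity recurs. It appears to belong to the first row of the other-AE block, and from 280 mg it would also give 140 mg. Section 9.2 stops treatment for an AE that prevents further dosing, but is not tied to any dose level. The deviation route in 5.3.1.4, "please consult the medical monitor to discuss for approval", applies when the investigator believes a departure from the guidance is needed. A site following the row and Table 3 may not think it is departing from anything.

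**After the fix.** From 560 mg the sequence is 560, 420, 280, and then at event 4 either discontinue or 280 mg again with medical-monitor approval. Neither option breaches the floor.

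**The case against.** The strongest reply is that the note governs. It is a prohibition, the row is only permissive, and 140 mg belongs in Table 3 because the two exceptions need it. On that reading the position at 280 mg is to withhold and not restart lower, with 9.2 and the medical monitor covering what follows. Most of this stands. The note is best read as controlling, and the 140 mg level is not itself a mistake. What remains is that Table 3 does not confine 140 mg to the exceptions, the hematologic row sends sites there without a limit, and the fallbacks name no action at 280 mg.

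A reader might go further and infer that the block gives no action at all at 280 mg. It does give one: withhold until recovery. Only the permitted step afterwards is missing.

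A reader might also infer that the floor makes discontinuation mandatory at 280 mg, so that Table 3 delays the stop by one event. The note does not say that. Withholding and then resuming at 280 mg would also respect it, and 6.1 permits growth factors and transfusion. Choosing between the two is a clinical decision.

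The comparison with other pathways has limits. The other-AE rows fit a 560 mg start; for a subject started at 280 mg, the 420 mg named at the second event would be an increase. Section 5.3.1.4 also allows a one-level reduction for other AEs, including Grade 2 events, without stating a stop. Finally, 5.3.1.1 refers sites to a pharmacy manual for dose modification on tablets, which was not available here. It might help sites, but the conflict within the protocol would remain.

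**Conclusion.** The point holds in a narrow form. The hematologic row and Table 3 lead to a dose that the note forbids, at the 2nd to 4th qualifying event depending on the dose held at the first. The 4th event (from 560 mg) and the 2nd (from a Child-Pugh A start) follow directly from the tables. The figures for subjects already reduced for other AEs rest on the stated reading of the original dose level.

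The number of subjects affected cannot be derived from the documents and is likely to be small. In Safety Run-in subjects, reductions for TLS or a DLT do not apply, so the issue falls mainly on randomized and treatment-naive subjects. The SAP describes randomization as done (section 4) and treatment-naive enrollment as complete (section 1), so correction helps only those still taking ibrutinib.

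There is no basis for extending this to the trial's inference. Safety analysis is descriptive (Protocol 10.6), the PFS estimand handles treatment discontinuation by treatment policy in all regions (SAP 4.1), and power and alpha do not depend on the dose ladder.

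**What to change.** In the next protocol amendment:

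1. Mark the 140 mg level in Table 3 as usable only under the note's two exceptions, and limit the hematologic Subsequent row to reductions no lower than 280 mg.
2. State the step for a further hematologic event at 280 mg. The sponsor should choose between discontinuing ibrutinib, which matches the other-AE sequence from 560 mg, and resuming at 280 mg after recovery with medical-monitor approval.

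The cost is small but not nil. Protocol 12.14 requires an amendment with ethics and site approval, so these lines are best carried in one already planned, with a memo to sites meanwhile if needed. If discontinuation is chosen, it is a new explicit stop, and a Child-Pugh class A subject started at 280 mg would reach it at the second event. Section 5.4 softens this by letting a subject who stops one drug for tolerability stay in the study on the other.

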5.3.1.5 Leukocytosis/Leukostasis

A high number of circulating white blood cells (> $400,000/\mu$ L) may confer increased risk of leukostasis; these subjects should be closely monitored. Administer supportive care such as hydration and/or leukapheresis as indicated. Ibrutinib may be temporarily held, and the medical monitor should be contacted.

5.3.1.6 Dose Modification for Hepatic Impaired Subjects

Ibrutinib is metabolized in the liver, and therefore subjects with clinically significant chronic hepatic impairment at the time of Screening (Child-Pugh class B or C) are excluded from study participation. See Appendix F for Child-Pugh classification.

• For subjects with existing chronic mild hepatic impairment (Child-Pugh class A) at enrollment, the starting dose has to be adjusted to a level of 280 mg daily (two capsules).

- For subjects who develop mild hepatic liver impairment while on study (Child-Pugh class A), the recommended dose reduction for ibrutinib is to a level of 280 mg daily (two capsules) unless lower doses had already been implemented.
- For subjects who develop moderate hepatic impairment while on study (Child-Pugh class B), the recommended dose reduction is to a level of 140 mg daily (one capsule).
- Subjects who develop severe hepatic impairment (Child-Pugh class C) must hold study drug until resolved to moderate impairment (Child-Pugh class B) or better.

Subjects who develop acute hepatic toxicity with liver enzymes Grade 3 or higher while on study should be managed per standard dose modification guidelines in Section 5.3.1.4.

5.3.2 Venetoclax

5.3.2.1 Formulation/Packaging/Storage

The individual study drug information is presented in Table 4.

Table 4. Identity of Venetoclax/Placebo Drug Product

Study Drug	Trademark	Formulation	Route of Administration	Manufacturer
Venetoclax/placebo	N/A	10 mg tablet Film coated	Oral	AbbVie
Venetoclax/placebo	N/A	50 mg tablet Film coated	Oral	AbbVie
Venetoclax/placebo	N/A	100 mg tablet Film coated	Oral	AbbVie

Packaging and Labeling

The venetoclax/placebo tablets will be packaged in blister packs during the initial dose ramp-up period and in high density polyethylene (HDPE) plastic bottles thereafter to accommodate the study design. Each container will be labeled as required per country requirements. Labels must remain affixed to the container.

Storage and Disposition of Study Drug

The venetoclax/placebo supplied in this study is for investigational use only, and must only be used within this study. All study drug must be maintained under adequate security and stored under conditions specified on the label until dispensed for subject use or returned to the Sponsor or representative.

The tablets must be stored at a controlled room temperature of 15° to 25°C (59° to 77°F).

5.3.2.2 Venetoclax Toxicity Management

Prophylaxis and Management of Tumor Lysis Syndrome

Venetoclax can cause rapid reduction in tumor and thus poses a risk for TLS in the Ramp-up Period. Changes in electrolytes consistent with TLS that require prompt management can occur as early as 6-8 hours following the first dose of venetoclax and at each dose increase. The risk of TLS is a continuum based on multiple factors, including comorbidities. Subjects with high tumor burden are at a greater risk of TLS when initiating venetoclax. Reduced renal function further increases the risk. The risk may decrease as tumor burden decreases with venetoclax treatment.

Tumor burden assessments, including radiographic evaluation (eg, CT scan) should be performed at Screening as well as blood chemistry assessments (creatinine, uric acid, potassium, phosphorus, calcium, and albumin, if available) in all subjects. Pre-existing abnormalities should be corrected prior to initiation of treatment with venetoclax.

The prophylaxis measures listed below should be followed and more intensive measures (including hospitalization) should be employed as overall risk increases:

Hydration: Ensure adequate hydration (1.5-2 L) 48 hours prior to initiating therapy with venetoclax and throughout the Ramp-up Period, especially on the first day of each ramp-up dose. Administer intravenous (IV) fluids as indicated based on overall risk of TLS or for those who cannot maintain adequate oral hydration.

Anti-hyperuricemic agents: Administer allopurinol within 72 hours prior to initiation of venetoclax; consider continuing through the Ramp-up Period. Rasburicase is recommended for subjects at high risk, especially those with high tumor burden.

Laboratory Assessments:

Pre-dose: Assess blood chemistries prior to initiating venetoclax to evaluate kidney function and correct pre-existing abnormalities. Reassess blood chemistries before starting each subsequent ramp-up dose of venetoclax.

Post-dose: For hospitalized subjects, monitor blood chemistries 4, 8, 12, 24 and, as needed, 48 hours after the venetoclax dose. For outpatient subjects, monitor blood chemistries at 6-8 hours and at 24 hours after the venetoclax dose. Electrolyte abnormalities should be corrected promptly (see Appendix H for Recommendations for Initial Management of Electrolyte Abnormalities and Prevention of Tumor Lysis). The next dose of venetoclax should not be administered until the 24-hour blood chemistry results have been evaluated. The same monitoring schedule should be followed when starting each subsequent ramp-up dose.

Hospitalization: Based on investigator assessment, subjects with high tumor burden (at least one lesion > 10 cm; or at least one lesion > 5 cm and circulating lymphocytes > 25,000 cells/mm³) and/or CrCl < 60 mL/min, are at greater risk of TLS and require hospitalization the first 24-48 hours of treatment at the 20 mg and the 50 mg ramp-up doses of venetoclax for more intensive prophylaxis and monitoring. Consider hospitalization for subsequent ramp-up doses based on reassessment of risk. During the course of the study, the DMC will review unblinded TLS data to determine whether continued hospitalization of these subjects is warranted.

